For records with a missing procedure date, the following procedure will be employed for use in determining whether the procedure is prior or concomitant:

- Procedure dates with a missing day and non-missing month will be assumed to occur on the first day of the non-missing month, except for

- procedures occurring in the month of first dosing, in which case the date will be the date of first dosing.
- Procedure dates with missing day and month will be assumed to occur on the first day of the non-missing year (i.e., January 1), except for procedures occurring in the year of first dosing, in which case the date will be the date of first dosing.

For records with a missing disease progression date from prior therapy, the following procedure will be employed for use in analyzing time to event endpoints:

- If the disease progression date is completely missing OR only the year is available, set as missing.
- If both year and month of disease progression date from are available and only day is missing, the date of disease progression will be imputed by the last day of the month.

For records with a partial death date, the following procedure will be employed for use in deriving time to event variables.

- The death date will be imputed by the earliest possible date that is not contradicting with any other available data in the database.

All other data will be reported as they are collected. No imputation methods will be used to replace missing data unless otherwise stated in this document.

D. Interim Analyses

This is a single-arm, open-label study, so interim analyses may be performed as the study progresses.

Details of analysis will follow each section described in this SAP, may including the following components:

- Disposition
- Protocol deviations
- Baseline characteristics: demographics, disease history, medical history, concomitant medication/procedure
- Key components from efficacy analysis
- Key components from safety analysis
- PK and pharmacodynamic data (as available)

E. Analysis Populations

1. Safety Population

The safety population includes participants who were enrolled, allocated to treatment, and received at least one dose of investigational product.

2. Efficacy Population

The efficacy population includes participants who received study drug and had an on-treatment response assessment (including “Not Evaluable”) or who discontinued study before any response assessment performed due to disease progression.

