All concomitant medications and dietary supplements received within 28 days prior to the first dose of study treatment through 30 days after the last dose of study treatment will be recorded in the eCRFs, using generic drug names when possible. Concomitant medications will be coded using World Health Organization (WHO) Drug version B3 Global March 2019 coding dictionaries and will be summarized by the anatomical main class (1st level) of each coded medication and, within that, the pharmacological subgroup (3rd level) of the coded medication. Patients are counted only once in each therapeutic class category. Concomitant medication will be summarized using the safety population and be tabulated for each dose level using frequencies and percentages. Percentages will be based on the number of patients in each dose level. A listing will be provided to display the indication, dose, units, frequency, route, start/end date of the medication.

Concomitant Procedure

Concomitant procedure is defined as any procedure with a start date prior to the date of the first dose of study treatment and continuing after the first dose of study treatment or with a start date between the dates of the first and last dose of study treatment. Any procedure with a start date after the date of the last dose of study treatment will not be considered a concomitant procedure. Any procedure with a stop date prior to the first dose of study treatment is defined as a prior procedure.

Concomitant procedure will be coded using Medical Dictionary for Regulatory Activities (MedDRA) version 22.0. System Organ Class (SOC) and Preferred Term (PT) will be summarized by number and percentage (%) of patients having at least one occurrence of a concomitant procedure. A listing will be provided to display the procedure reason, location, and time.

VII. Efficacy Analyses

Efficacy analyses will be performed on Efficacy Population. Efficacy analyses will be descriptive in nature. Summary tables and figures will be presented by dose cohorts within the dose escalation and investigational arms.

A. Definition of Efficacy Outcomes

1. Assessment Method

The response of SYNB1891-injected lesion(s) and an overall response of up to 5 non-injected target lesions will be assessed using RECIST 1.1 (Eisenhauer et al 2009), iRECIST (Seymour et al 2017), or LYRIC (Cheson et al 2016) at

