Patients’ best overall response will be selected based on the overall response order (CR, PR, SD, PD, NE for RECIST; CR, PR, SD, PD, IR1, IR2, IR3 for LYRIC) through the study. Objective Response Rate (ORR), defined as the proportion of patients’ overall response achieving a PR or CR at any time on the study, will be summarized descriptively by arm and cohort. In addition, an exact 90% confidence interval (CI) will be presented for RP2D cohort in Arm 2. Note that the definition of the Efficacy Population includes all treated patients who have an on-treatment response assessment or who discontinued study early due to disease progression; therefore, all Efficacy Population patients will be included in the denominators for percentage even if the patient had a Not Evaluable response. The best overall response and objective response rate will be summarized separately for each assessment method (RECIST, iRECIST, or LYRIC).

Similarly, the proportion of patients with a PR and the proportion of patients with a CR at any time during the study will be summarized as part of the best

overall response. The sum of diameters and change from baseline will also be summarized, by arm and cohort at each assessment visit.

All overall tumor and lymphoma response data will be presented in patient listings.

3. Determination of Time to Event Endpoints

Below is a list of events definitions for the solid tumor patients with a confirmed response according to RECIST v1.1 and iRECIST, and lymphoma patients with response according to LYRIC. The number of events and the number of censored patients will be summarized. The median time to event (reported in days) and the 25th and 75th percentiles on the time to event for each arm and cohort will be summarized using Kaplan-Meier estimates. Progression-Free Survival graphs will also be provided.

When calculating the endpoint that involve PD diagnosis date, such as time to progression or progression free survival, below rules will apply to account for the repeated PD response assessment per iRECIST:

- When a patient has disease progression per RECIST, if the repeated assessment confirmed as disease progression according to iRECIST criteria, the first PD date will be used in the endpoint calculation.

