- If the repeated assessment confirmed as no disease progression and later SD, PR or CR occur, the initial diagnosis of PD will not be considered as the endpoint. Patients will continue further assessments until consecutive disease progression assessments occur.
- If the repeated assessment confirmed no disease progression and no later SD, PR or CR occur, and patients stop treatment due to not clinically stable or the patients die from their cancer, then the first unconfirmed progression should still be used as the endpoint (Seymour et al 2017).
- If the patients do not do a repeat assessment due to any other reasons, the unconfirmed PD date will be used as the endpoint.

For patients with lymphoma and evaluated by LYRIC, if they are categorized as having any of the IR response, repeat imaging should be obtained after an additional 12 weeks.

- If a patient is assessed as having IR and then “true” progressive disease at a subsequent time point, the IR assessment should subsequently be corrected to progressive disease and the date will be used as the PD endpoint for the relevant time to event analysis,
- If repeated imaging could not be obtained, the IR category will still be used as the endpoint.
- **Time to Progression (TTP):** defined as the time from the first SYNB1891 injection (Day 1) to PD. Patients who complete the study without PD or death will be censored at the day of their last visit. Patients

who discontinue or die due to disease progression, the endpoint will be the last assessment date prior to discontinue or death. Patients who discontinue or die not due to disease progression will be censored at their last tumor assessment.

- **Progression Free Survival (PFS):** defined as the time from the first SYNB1891 injection (Day 1) to PD or death, whichever is first, from any cause. Patients who complete or discontinue the study without disease progression or death will be censored at the last Response assessment date.

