- **Duration of Response:** defined as the time from the first day the patient achieves objective response (PR or CR) to the day the patient's response falls to PD. Patients who do not achieve an objective response of a PR or CR during the study are excluded from this analysis. Patients who achieve objective response and remain the response at the end of the study will be censored at their last tumor assessment visit. If patients discontinued study due to disease progression after achieving objective response, they will not be censored, and disease progression date will be the endpoint. If patients discontinued study not due to disease progression after achieving objective response, they will be censored at their last tumor response assessment date.

Waterfall plots for tumor response by individual will be presented. The plots will have one bar per subject sorted from worst to best response with color by dose administered. Tumor response will be calculated based on the type of cancer that the patient has with the appropriate measure using either RECIST or LYRIC; an indicator will be placed on the figure to show if the response for each subject is from “R”, RECIST, or “L”, LYRIC. One waterfall plot will indicate best tumor response (minimum percent change from baseline) at any time point for each subject. One waterfall plot will represent injected and non-injected tumors.

Spaghetti plots for tumor response by time will be presented. One line will be drawn per subject with color by response type (see Section VII.2). The horizontal axis will be time and the vertical axis will be percent change from baseline in tumor response. One spaghetti plot will be generated for all patients at all times. One set of spaghetti plots will be generated with one panel per analysis type (RECIST/ iRECIST, or LYRIC) and only patients who apply for the current analysis type will be shown.

Swimmer plots will be generated with panels by analysis type (RECIST/iRECIST, or LYRIC). The plots will have one horizontal bar per subject firstly sorted by best response type (see Section VII.2), and then sorted by from best to worst time to start that response; when best to worst time to start that response does not apply (e.g. NE for RECIST), patients will be sorted by

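### The lead-in to the time-to-event section ties TTP and PFS to responders, contradicting the Efficacy Population and the endpoints' own definitions

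*SAP*

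**What the plan says.** The first sentence of SAP VII.A.3 (Determination of Time to Event Endpoints) presents a "list of events definitions for the solid tumor patients with a confirmed response according to RECIST v1.1 and iRECIST" and, for the other disease group, "lymphoma patients with response according to LYRIC". The same paragraph then plans event and censoring counts, Kaplan-Meier medians and quartiles for each arm and cohort, and PFS graphs. The list that follows is TTP, PFS and DOR.

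Other parts of the SAP bear on who is analyzed:

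- Section VII, opening: "Efficacy analyses will be performed on Efficacy Population".
- Section V.E.2: that population takes in patients with an on-treatment assessment, including not-evaluable results, "or who discontinued study before any response assessment performed due to disease progression".
- VII.A.3, TTP: "defined as the time from the first SYNB1891 injection (Day 1) to PD. Patients who complete the study without PD or death" are then given a censoring rule. PFS also starts at the first injection and ends at progression or death from any cause.
- VII.A.3, DOR: patients without a PR or CR "during the study are excluded from this analysis".
- VII.A.2, ORR: the proportion of patients "achieving a PR or CR at any time on the study".
- Appendix 5: Tables 15 to 18 (TTP and PFS) and Tables 19 and 20 (DOR) all carry the Efficacy population label. Tables 15 to 18 are also marked for the interim analysis at the end of Arm 1.

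**The concern.** A responder restriction suits DOR, whose clock starts at the response. It does not suit TTP or PFS, whose clock starts at the first injection. To enter a responder-only set, a patient must first remain free of progression and alive until a scan shows the response. That waiting time is then counted as progression-free time, which is immortal-time bias. Patients who progress early or never respond drop out, and the curve no longer describes the treated cohort.

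A second problem concerns solid tumors. ORR requires only a PR or CR at some time. If the lead-in governs DOR, DOR requires a confirmed response, so the response rate and the durations reported beside it could refer to different patients.

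The SAP states that it governs the analysis. A programmer who takes the section-specific sentence over the general population statement would be following the document.

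**Working it through.** **Step 1. Compare the lead-in with the rest of the SAP.**

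| Place | What it implies for TTP and PFS |
|---|---|
| VII.A.3 lead-in | Responders only (confirmed, for solid tumors) |
| Section VII and V.E.2 | Efficacy Population, including patients who can never be responders |
| TTP and PFS bullets | No response condition |
| Progression-date rules in VII.A.3 | Cover patients whose initial scan result is progression, including those never rescanned |
| DOR bullet | Excludes non-responders from DOR only; redundant if the lead-in already did so |
| Appendix 5, Tables 15 to 18 | Efficacy label; not decisive, because responder-only DOR Tables 19 and 20 carry it too |

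The lead-in stands alone against four of the other five rows, and the fifth is neutral. Protocol 10.3 also plans to describe lack of progression as well as response, across all evaluated tumors, and lack of progression includes stable disease.

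**Step 2. Check the term.** The SAP has no rule for confirming a CR or PR. In VII.A.1 and VII.A.3, confirmation concerns progression under iRECIST. The lymphoma clause does not use the word.

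**Step 3. Sample size.** The documents give no planning figure for TTP, PFS, DOR or ORR. The only planning number is about 70 patients. With 3 patients plus 1 replacement per cohort, up to 7 and 5 cohorts, and 20 in expansion: 7 × (3 + 1) + 5 × (3 + 1) + 20 = 68. This agrees with about 70 and with the design figure's 28 + 20 + 20 = 68.

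**Step 4. Earliest event under the literal reading.** Cycles last 21 days and the first scheduled on-study imaging is at the end of Cycle 2: 2 × 21 = 42 days. SAP IV.B puts it at the start of the next cycle, which is practically the same date. A responder must reach that scan without progression or death. Clinically indicated scans (protocol Appendix 1) or an early end-of-treatment scan could come sooner, so events before about Day 42 would be rare, not impossible. Any confirmation requirement moves this later.

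**Step 5. Patients left under the literal reading.** Since no response rate is given, I assume p from 5% to 30%. The expected number of responders among n patients is n × p. The chance of none is (1 − p)^n.

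| Assumed p | Chance of none in a 3-patient cohort | Expected in 20 expansion patients | Chance of none in 20 | Expected in 68 |
|---|---|---|---|---|
| 5% | 0.857 | 1 | 0.358 | 3.4 |
| 10% | 0.729 | 2 | 0.122 | 6.8 |
| 20% | 0.512 | 4 | 0.012 | 13.6 |
| 30% | 0.343 | 6 | 0.001 | 20.4 |

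At 10% to 20%, a 3-patient cohort would more often than not have nobody to analyze, and the expansion cohort would have 2 to 4 patients. If only some responses were confirmed, there would be fewer.

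**The case against.** The strongest reply is that the lead-in introduces definitions and does not set an analysis population. The population is set in Section VII and contains patients who cannot be responders. The TTP and PFS bullets carry no response condition, the progression-date rules would be largely pointless in responders, and the separate DOR exclusion would be superfluous. The phrase may simply mean a confirmed response assessment, because the SAP uses response for every category, progression included.

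Much of this stands. A reader might infer that the SAP as it stands does estimate TTP and PFS in responders only. The documents do not support that: the weight of the text points to the full Efficacy Population as the intent.

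Two parts do not stand. The table labels do not settle the matter, because the responder-only DOR tables carry the same one. Nor does reading the phrase as a confirmed assessment reconcile the sentence with the rest: the Efficacy Population includes patients with no scan, and the rules count some unconfirmed progressions as events.

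A reader might also infer that PFS would be guaranteed to exceed 12 weeks, taking confirmation at the next scheduled scan (4 × 21 = 84 days). The SAP states no confirmation interval for response, clinically indicated scans are allowed, and the lymphoma clause does not ask for confirmation. Only the weaker statement, about Day 42 on scheduled imaging, can be made.

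The mismatch between DOR and ORR is likewise conditional. The DOR bullet uses PR or CR, as ORR does; the two diverge only if the lead-in overrides it.

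**Conclusion.** The concern holds as a contradiction within the SAP. The lead-in uses an undefined term and, taken literally, prescribes a biased analysis set for TTP and PFS that conflicts with the stated population and with the endpoints' own definitions.

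The consequence if it were followed is large for these endpoints: almost no events before about Day 42, and 2 to 4 analyzable patients out of 20. The patient count rests on an assumed response rate of 10% to 20%. The timing rests on scheduled imaging.

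The consequence for the trial is limited. SAP Section II lists TTP, PFS and DOR as exploratory, and Section VII makes efficacy descriptive. The primary DLT endpoint and the dose decisions do not depend on them. The correction should be made because it costs little and the present sentence could make the PFS and TTP summaries uninterpretable.

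**What to change.** Replace the population wording in the first sentence of SAP VII.A.3 with:

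*TTP and PFS are estimated in the Efficacy Population; DOR is estimated in Efficacy Population patients with an objective response (PR or CR) as counted in ORR.*

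The text should name the Efficacy Population, not all treated patients; the latter would create a new conflict with Section VII and with Tables 15 to 18. If the sponsor wants DOR to require a confirmed response, the SAP should define confirmation for CR and PR, including the interval, and say how that set relates to ORR.

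The cost is one SAP sentence, plus a definition only if confirmation is kept. No data collection, table list or sample size changes. It should be settled before the end-of-Arm-1 interim, when the TTP and PFS tables are first due.

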It is recognized that “clinical deterioration” is subjective. In some cases, the simple growth of a nodal or tumor mass could worsen the symptoms mechanically related to that mass, such as pain at the tumor site, compression of adjacent structures, etc. Such an increase in symptoms that can be directly attributed to the size of the tumor mass may not be considered as clinical deterioration in this context. However, in most cases, patients should be experiencing clinical stability or improvement by Investigator assessment to be considered as having IR, and in all cases, the patient must be considered likely to tolerate continued treatment and not at risk of serious complications should further tumor growth occur.

2. **Appearance of new lesions or growth of one or more existing lesion(s) $\geq 50\%$ at any time during treatment; occurring in the context of lack of overall progression (< 50% increase) of overall tumor burden, as measured by SPD of up to 6 lesions at any time during the treatment [IR(2)].** This phenomenon may occur early or late in the treatment course, and therefore, unlike IR(1), is not defined by its temporal relationship to treatment initiation. Both within and outside the context of clinical trials, a biopsy is strongly encouraged in such cases. If the biopsy does not confirm the presence of viable tumor in the new or enlarging lesion(s), then the lesion(s) are not considered active disease and should not be used in subsequent SPD assessments.
3. **Increase in FDG uptake of 1 or more lesion(s) without a concomitant increase in lesion size or number [IR(3)].** Increased immune activity at the site of tumor may manifest as an increase in FDG uptake. Therefore, by itself, changes in uptake should not trigger an assignment of progressive disease with checkpoint inhibitors. The magnitude of increase in uptake in an immune-mediated flare compared with that in true tumor progression is not yet known. It is important to investigate this finding, especially in conjunction with biopsies of the lesion in question.

An increase in FDG avidity of 1 or more lesions suggestive of lymphoma, without a concomitant increase in size of those lesions meeting progressive disease criteria does not constitute progressive disease.

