It is possible that, at a single time point, a patient could fulfill criteria for both IR(1) or IR(2) and IR(3): for example, there could be a new FDG avid lesion in the absence of overall progression [IR(2)], and, at the same time, increase in FDG uptake of a separate lesion [IR(3)]. In such cases, the designation of IR(1 or 2) should take priority [e.g., IR(2)] in the above example.

In patients categorized as having any of the above types of IR, repeat imaging should be obtained after an additional 12 weeks (or earlier if clinically indicated). At that time, response should be re-evaluated, and the patient should be considered to have true progressive disease if the SPD of target lesion has increased further, with the considerations below:

- In the case of IR(1), the comparison should be between the first IR(1) and the current SPD, with an increase of $\geq 10\%$ constituting progressive disease. In addition, there should be an increase of ≥ 5 mm (in either dimension) of ≥ 1 lesion for lesions ≤ 2 cm and 10 mm for lesions > 2 cm. The 10% threshold is empiric but designed to account for variability in measurement, especially when taken along with the minimum increase. If the target SPD increase is $< 10\%$, the response would still be categorized as IR(1), and the patient could continue treatment until a subsequent scan shows either true progressive disease [$\geq 10\%$ increase from first IR(1) time point and an increase of > 5 mm in either dimension of ≥ 1 lesion] or response ($\geq 50\%$ decrease from baseline). In this situation, it is reasonable to repeat imaging in 4 to 8 weeks of the original IR(1) time point to ensure absence of significant further increase.
- In the case of IR(2), the new or growing lesion(s) (unless biopsy proven to be benign) should be added to the target lesion(s), up to a total of no more than 6 total lesions. If the SPD of the newly defined set of target lesions has increased $\geq 50\%$ from their nadir value (which may precede the IR time point), the patient should be considered to have progressive disease.
- In the case of IR(3), because inflammatory responses may result in an increase in the standardized uptake value of a lesion, the patient will not be considered to have PD unless there is evidence of PD by an increase in lesion size or the development of new lesions, as noted above.

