Importantly, if a patient is assessed as having IR and then “true” progressive disease at a subsequent time point (without an intervening objective response between IR and progressive disease), the IR assessment should subsequently be corrected to progressive disease for reporting purposes to the date of the prior designation of IR. While these lesions may remain stable during the time of observation, the initial designation of IR should be changed to progressive disease.

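### The SAP back-dates lymphoma progression to the earlier immune-response (IR) scan without the protocol's no-intervening-response condition, and its missing-imaging rule takes in IR(3), which the protocol says is not progression

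*SAP*

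**What the plan says.** SAP VII.A.3 (Determination of Time to Event Endpoints) sets the LYRIC rules for lymphoma patients. They apply to all IR types alike: "if they are categorized as having any of the IR response, repeat imaging should be obtained after an additional 12 weeks". Two rules follow.

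- IR and then true progression: "the IR assessment should subsequently be corrected to progressive disease and the date will be used as the PD endpoint". The sentence goes on to apply this to whichever time-to-event analyses are relevant.
- No repeat scan: "If repeated imaging could not be obtained, the IR category will still be used as the endpoint".

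Protocol Appendix 3 is the source of the first rule but attaches a condition: "without an intervening objective response between IR and progressive disease), the IR assessment should subsequently be corrected to progressive disease for reporting purposes", and the date moves "to the date of the prior designation of IR".

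On IR(3), where FDG uptake rises without growth in lesion size or number, Appendix 3 is explicit. Higher uptake without an increase in the "size of those lesions meeting progressive disease criteria does not constitute progressive disease". At the repeat assessment, "the patient will not be considered to have PD unless there is evidence of PD by an increase in lesion size" or by new lesions.

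SAP I.B makes the SAP the governing document for the analysis.

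**The concern.** Two SAP rules depart from the response criteria that the protocol adopts.

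The first concerns delayed responders. LYRIC exists so that a flare on an early scan does not end a patient's record before a later response can show. If an IR is followed by CR or PR and then by relapse, the protocol leaves the progression date at the relapse. The SAP rule, lacking the condition, places it at the flare.

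The second concerns patients with IR(3) and no repeat scan. The protocol says that they have not progressed; the SAP appears to give them an event.

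At stake are the LYRIC summaries of TTP, PFS and DOR (SAP Appendix 5, Tables 16, 18 and 20). Tables 16 and 18 are also planned for the interim analysis at the end of Arm 1.

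**Working it through.** The documents give no figure to reproduce here. The check compares the texts and then applies the SAP's date rules to an illustrative patient.

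**Inputs from the documents**
- Cycle length is 21 days (protocol 4.2.1). Imaging is at the end of every even-numbered cycle (protocol 7.3), so scans fall every 2 × 21 = 42 days, or 6 weeks.
- The repeat scan after an IR is due 12 weeks later (SAP VII.A.3; protocol Appendix 3).
- TTP and PFS start at the first injection, Day 1. DOR starts at the first PR or CR and ends when the response drops to PD (SAP VII.A.3).
- Durations are stop minus start plus 1 (SAP V.F).

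**Assumed patient:** IR at week 6 (day 42), PR at the 12-week repeat scan in week 18 (day 126), true progression at week 42 (day 294). All three are scheduled scan times.

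**Progression date**
- Protocol: a PR intervened, so the condition for back-dating fails and PD stays at week 42. TTP = PFS = 42 weeks.
- SAP, with *the date* read as the IR date: PD is at week 6. TTP = PFS = 6 weeks.
- Difference: 42 - 6 = 36 weeks. The event itself is genuine under both.

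**DOR, if the same PD date is used**
- Protocol: 42 - 18 = +24 weeks (294 - 126 + 1 = 169 days).
- SAP: 6 - 18 = -12 weeks (42 - 126 + 1 = -83 days).
- Whenever the IR precedes the first response, IR date minus response date is negative however long the response lasted. At the shortest scan gap (IR day 42, response day 84) it is 42 - 84 + 1 = -41 days.

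**Can *the date* mean the true-progression date?** That would remove the negative DOR. But the SAP would then contradict Appendix 3 for every patient without an intervening response, whom the protocol does back-date. Neither reading matches the protocol in both situations.

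**Does another SAP rule restore the condition?** The same section drops an initial PD that is followed by SD, PR or CR, but those rules are introduced as accounting for repeat assessment per iRECIST. The LYRIC rules follow separately and contain no equivalent.

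**Un-reimaged IR(3), illustration.** Assume four true PFS events at days 84, 126, 168 and 210, plus IR(3)-only patients last scanned at day 42.
- Censored at day 42, one or two such patients: S(84) = 3/4 = 0.75.
- One counted as an event: S(84) = 4/5 × 3/4 = 0.60.
- Two counted as events: S(84) = 4/6 × 3/4 = 0.50.

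Here the time is the same and only the status changes, from censored to event.

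**The case against.** Several stronger readings are tempting, and the documents do not support them.

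- **Negative DOR is certain.** It is not. The DOR definition ends the interval when a response falls to PD, which presupposes that the response came first, and it uses the progression date for patients who stop for progression after responding. On that text alone DOR would end at week 42. The two SAP rules therefore conflict, and the phrase limiting the re-dating to relevant analyses does not settle which one governs DOR.
- **The SAP expressly overrides an intervening response.** It is silent on that case. The effect comes from an omitted condition, and *the date* is undefined; the IR date is the natural reading because the protocol sentence it follows says so.
- **The SAP states that IR(3) is progression.** It says that the IR category is the endpoint, and elsewhere (SAP VII.A.1 and VII.A.2) it keeps IR1 to IR3 distinct from PD. The PD reading rests on the setting, a list of rules for PD dates, and on the parallel iRECIST rule, which uses an unconfirmed PD date when no repeat scan is done.
- **Any IR(3) patient who stops becomes a false event.** The rule applies only when repeat imaging could not be obtained. Some who stop will be scanned at a scheduled visit or at end of treatment, although protocol 7.3 waives the latter if imaging was done in the preceding 8 weeks.
- **One such case changes a cohort median.** Not in general: with PFS of 6, 6 and 42 weeks, moving 42 to 6 leaves the median at 6.

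It is also fair to say that these endpoints are exploratory, that efficacy is descriptive, that dose decisions rest on Cycle 1 DLTs, and that response data are listed by patient, so a misdated case could be spotted. All of this limits the consequence. It does not supply the missing condition or exempt IR(3).

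**Conclusion.** The point holds, and the SAP should be changed. The omitted condition is a plain difference from Appendix 3. On its natural reading it dates a real progression too early for a lymphoma patient who goes from IR to response to progression: 6 weeks instead of 42 in the example. For DOR, the finding is a conflict between two SAP rules that yields an impossible value under one of them. For IR(3), the finding is a rule that covers a category the protocol says is not PD and that, read in context, turns a censored patient into an event.

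The numbers rest on assumed patient dates placed on the scheduled scans. The number of lymphoma patients is not given, so how many would be affected cannot be computed. The reach is limited to the LYRIC TTP, PFS and DOR summaries; the primary endpoint and dose-finding are untouched.

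**What to change.** Replace the two LYRIC rules in SAP VII.A.3 with text to this effect:

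1. *If true PD follows IR with no CR or PR recorded in between, the PD date is the date of the prior IR designation. If a CR or PR intervened, the PD date is the date of true PD. This applies to TTP, PFS and DOR.*
2. *IR(3) alone without repeat imaging is not a PD event; the patient is censored at the last response assessment date unless death (for PFS) or PD is otherwise documented. For IR(1) or IR(2) without repeat imaging, the IR date is used as the PD date.*

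The last sentence keeps the existing handling of IR(1) and IR(2), read as above, but states it openly. The censoring date matches the one already in the SAP's PFS definition.

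The cost is two short edits and the matching derivation in the programs, with no new data. They should be made before the end-of-Arm-1 interim, which includes Tables 16 and 18.
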